5.7.6 Exploratory Efficacy Endpoints

Any p-values presented for exploratory efficacy endpoints are for descriptive purposes only.

5.7.6.1 Functional Disability Scale at 24 Hours

Data will be analyzed in the same manner as described in Section 5.7.4.4. However, in this case the analysis uses the data from the 24 hour post-dose time point.

5.7.6.2 Pain Relief at 30, 60 and 90 Minutes Post-Dose

Pain relief at 30, 60, and 90 minutes post-dose will be assessed by tabulating the number of mITT subjects that report a pain level of none or mild (responses of 0 or 1 on the 4-point Likert scale) at the specified post-dose time point by treatment group. Subjects with missing data at the specified post-dose time point will be imputed as failures (NC=F).

First, the data will be evaluated at each time point for each time point, using the first analysis methods described in Section 5.7.3.1.

Pain relief over time up to 2 hours will be analyzed using Kaplan-Meier methods. Kaplan-Meier estimates will be tabulated using the following time periods (0 through 30 minutes, > 30 through 60 minutes, > 60 through 90 minutes, > 90 through 135 minutes, and >135 minutes).

For each time period, the number of subjects at risk, with an event (pain relief), censored, and survival probability estimate (with 95% CI), will be presented by treatment group. Subjects who never reach mild or no pain by 135 minutes, will be censored at 136 minutes. Additionally, subjects who take rescue medication prior to 135 minutes will be censored at the date/time associated with their rescue medication. Note that the probability of survival corresponds to the probability of NOT having pain relief. Survival estimates are calculated using the Kaplan-Meier product-limit method and median survival (time to pain relief), and will be presented along with 95% CIs calculated using the method of Brookmeyer and Crowley.

To support the analysis, a Kaplan-Meier plot, with time in minutes on the x-axis and probability of survival on the y-axis, will be presented by treatment group. The number at risk at each time point (0, 15, 30, 45, 60, 90, and 135) minutes will be presented below the figure. In this analysis, being at risk corresponds to not yet having had pain relief; therefore, the subject is still "at risk" of having pain relief. Once a subject has pain relief or is censored, then the subject is no longer in the risk pool. If a subject has missing data at an earlier time point, then the time point with missing data is not considered. The subject is still considered at risk of failure at a future time point if data are available. Subjects are censored as described above.

5.7.6.3 Preference of Medication (PoM)

The PoM is a brief scale that captures the subjects' perception of whether the medication they are taking has had a greater benefit compared with previous medications to treat their pain. Responses at 24 hours post-dose for all subjects who provided a response, and answered "yes" to the lead-in question (i.e. "Have you ever taken migraine medication") will be tabulated. The number and percentage of subjects preferring the study medication, along with 95% asymptotic CIs, are presented by treatment group. The tabulations will be repeated for the subset of subjects considered as responders and non-responders by treatment group without imputation. Responders are those subjects who reported a pain score of 0 or 1 at 2 hours post-dose and who did not require rescue medication at or prior to 2 hours post-dose.

5.7.6.4 Migraine Quality of Life Questionnaire (MQoLQ)

Impact of treatment on patient-reported quality of life is assessed using the MQoLQ, which is a 15-item instrument that has been validated in migraine patients to measure the short-term impact of treatment (within 24 hours). The MQoLQ consists of 15 items across the following five domains: (1) work functioning, (2) social functioning, (3) energy/vitality, (4) migraine symptoms, and (5) feelings/concerns. There are three items within each domain. Response options for each of the items are on a 7-point scale where 1 indicates maximum impairment of QoL and 7 indicates no impairment. Each domain has a maximum score of 21 and a minimum score of 3. The items in the work functioning domain are: (1) ability to do normal everyday work, (2) ability to operate machinery or a motor vehicle, and (3) ability to stay alert. The items in the social functioning domain are: (1) interactions with people who are close to you, (2) interactions with other people, and (3) ability to enjoy life. The items in the energy/vitality domain are: (1) energy level, (2) ability to have a good night's sleep, and (3) mood. The items in the migraine symptoms domain are: (1) have throbbing head pain, (2) have increased sensitivity to light and/or noise, and (3) have nausea. Lastly, the items in the feelings/concerns domain are:

(1) feel upset about having migraine headaches, (2) feel physically uncomfortable, and (3) feel concern that your migraine medication wouldn't relieve your migraine headache symptoms.

The observed responses at 24 hours post-dose will be presented for each item, each domain, and as a total score, by treatment group. The observed responses at 24 hours will also be summarized as a continuous response for each item, domain, and for the total score. Responses will also be presented in a by-subject listing along with treatment group, historical MBS collected at screening, MBS reported at migraine onset, migraine severity just prior to study medication, and migraine severity at 24 hours post-dose.

5.7.6.5 Additional Tabulations

Pain freedom, pain relief, freedom from MBS, and functional disability score will be tabulated by treatment group at each post-dose time point. Success for each of these endpoints will be tabulated using the mITT subjects.

Freedom from nausea, freedom from phonophobia, freedom from photophobia, and functional disability scale response will be tabulated by treatment group at each post-dose time point. The tabulation will include: the total number of subjects reporting each of the above symptoms at baseline, success as the percentage of the total number of subjects reporting the symptoms at baseline, and the number of subjects that reported the symptom but with missing data at the post-dose time point as a percentage of the number reporting the symptom at baseline.

5.7.6.6 Sheehan-Suicidality Tracking Scale (S-STS)

The S-STS is a prospective, self-reported rating scale that contains 16 questions to track both treatment-emergent suicidal ideation and behaviors. In the event the subject is unavailable, the S-STS clinician-administered rating scale will be completed that contains 6 yes/no questions.

Self-reported S-STS scores are calculated as follows:

- Ideation subscale score: Sum of scores (0-4) for Questions 2-11
- Behavior subscale score: Sum of scores (0 4) for Questions 1a, (highest of 12 or any row of 16), (highest of 14 or any row of 15), 17, and 20
- Total score: Sum of the ideation and behavior subscale scores

The self-reported S-STS ideation subscale, behavior subscale, and total score will be summarized at baseline and the change from baseline (i.e., <-1, -1, no change, 1, >1) will be summarized at the end of treatment visit.

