¹ **Screening/Baseline Phase** will be 3 - 28 days. The **Baseline Visit** may be scheduled but should only occur *after* all screening procedures are complete, patient meets inclusion/exclusion criteria, and lab test results have been received by the site.

² Patients will use eDiary to answer questions about their migraine symptoms upon experiencing a moderate/severe migraine headache. The patient will administer pre-dispensed study drug if 1) the headache remains moderate or severe; 2) the patient has completed all required migraine assessment questions in the eDiary, including their current most bothersome migraine symptom, and 3) the patient has not already taken prohibited medications (see protocol section 5.4).

³ Patients should keep track of their concomitant medications throughout the study and report them to the study personnel at the End of Treatment Visit. Any medication taken for recurrent headache should be documented. Use of concomitant medications after randomization, including rescue medications, will be recorded by the patient on a paper diary and reported to the site.

⁴ Height will only be captured at the Screening Visit. Weight body temperature, respiratory rate, blood pressure and heart rate will be collected at all time points where indicated. Sitting arterial systolic and diastolic blood pressure and pulse rate will be measured.

⁵ All Screening Visit laboratory test results must be received prior to Baseline Visit.

⁶ A serum pregnancy test will be completed at Screening and End of Treatment Visits as part of the standard laboratory tests (if appropriate). Confirmatory urine pregnancy test for WOCBP should be completed on site at Baseline Visit and any subsequent visits for confirmation at the Investigator's discretion. Home pregnancy test will be provided to WOCBP after completion of baseline visit.

⁷ SAEs are reported from the time of informed consent and non-serious AEs are reported from baseline. All ongoing non-serious AEs and SAEs will be followed to resolution or until investigator deems there will be no further status change. SAE and AE's that occur during the treatment period should be reported to the site.

⁸ This scale will be clinician administered, completed on site, and will be in paper. The source document will be provided by Biohaven. The assessment period for completing the scale will be 30 days prior to Screening, and since the last visit for the remainder of the study.

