6 STUDY CONDUCT AND DESCRIPTION OF STUDY PROCEDURES

6.1 Study Materials

The following study materials will be provided at the study start:

- Investigator File/Regulatory Binder
- Pharmacy Binder
- Drug Accountability Logs
- Sample source documents, where applicable
- Concomitant and Rescue Medication Logs (take home for patient)
- Investigator Brochure
- Interactive Web-based Response System (IWRS)
- Electronic Case Report Form (eCRF) instructions
- Electronic Diary (eDiary): 1 will be given to each randomized patient
- Instructions for the ePRO device and access to the portal
- Laboratory Kits and Laboratory Manual
- Home Pregnancy Test
- ECG Machine and Instructions
- Serious Adverse Event (SAE) forms
- Pregnancy Surveillance Forms

All sites will use an Electronic Data Capture (EDC) tool to submit study data to Sponsors CRO. Electronic Case Report Forms (eCRFs) will be prepared for all data collection fields including Serious Adverse Events (SAE) Reporting. SAE data (including responses to queries) will be submitted to the CRO using eCRFs. Electronic Patient Reported Outcomes (ePRO) will be used for all patient-rated scales and will be captured on an eDiary. Any assessment completed by the patient in the eDiary will be transferred from the site/patient to the vendor and from the vendor to the CRO and/or sponsor. No additional source documents are required for scales and assessments completed by the patient in eDiary.

Safety laboratory, plasma, serum, instructions for all specimens collected will be provided by a designated central laboratory. ECG equipment, supplies, instructions and training materials will be supplied by a centralized ECG vendor.

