6.2.4 Laboratory Assessments

6.2.4.1 Safety Laboratory Testing

Blood and urine samples will be obtained as outlined in [Table 1](#) for clinical laboratory evaluations. A central laboratory vendor will be utilized for this study and a laboratory manual will be provided to each site. **If possible, patients should be fasting for a minimum of 8 hours prior to all blood draws.** However, if a patient is not fasting at a given visit, the blood draw should still be performed, and the non-fasting status should be documented.

Hematology: Hemoglobin, hematocrit, red blood cell count, white blood cell count (WBC) with differential, and platelets

Blood chemistry/electrolyte: Sodium, potassium, chloride, bicarbonate, calcium; glucose, BUN (urea), serum creatinine, uric acid, ALT, AST, alkaline phosphatase, LDH, total protein, albumin, total bilirubin, direct bilirubin, indirect bilirubin, CPK (with local lab fractionation, if central lab CK result is $> 1.5 \times \text{ULN}$);

Lipid panel: Cholesterol, LDL, HDL, triglycerides (Screening Only).

Estimated glomerular filtration rate: eGFR using the estimated MDRD formula will be calculated and reported by the central lab at each visit that clinical laboratory tests are collected as outlined in [Table 1](#).

Urinalysis: pH, specific gravity, ketones, nitrites, urobilinogen, leukocyte esterase, protein, glucose and blood. If blood, protein or leukocytes are positive, reflex to microscopic examination.

Urine Drug Screen: For drugs of abuse

6.2.4.2 *Pregnancy Testing*

Pregnancy tests will be conducted (serum, urine, or home pregnancy test), if appropriate prior to randomization, and as outlined in [Table 1](#).

6.2.5 **Sheehan Suicide Tracking Scale**

The Sheehan STS is a prospective, patient self-reported or clinician administered rating scale that contains 16 questions to track both treatment-emergent suicidal ideation and behaviors [16, 17]. If the investigator determines that a subject is at risk of suicide or self-harm, appropriate measures to ensure the subject's safety and obtain mental health evaluation must be implemented. The subject must immediately be discontinued from the study. The event should be recorded as either an AE or SAE as determined by the investigator and reported within 24 hours to the Sponsor.

6.3 **Efficacy Assessments**

6.3.1 **Pain**

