2.3.3 Exploratory Estimands

The estimands corresponding to the exploratory objectives are shown in Table 3.

Objective	Functional Disability at 24 hours	
Population	mITT	
Variable	Percent of subjects with a response of "normal" at 24 hours post-dose	
Intercurrent Events	NC=F; RM=F	
Pop. Summary	Percentage within each treatment group (BHV3000 & Placebo)	
Objectives	Pain Relief at 30, 60 or 90 minutes post-dose	
Population	mITT	
Variable	Percent of subjects who report pain as mild or none at the time point of interest	
Intercurrent Events	NC=F; RM=F	
Pop. Summary	Percentage within each treatment group (BHV3000 & Placebo)	
Objectives	Preference of Medication	
Population	Treated subjects who: 1) answer "yes" to the lead-in question (i.e. "Have you ever taken migraine medication?") and provide preference of medication data	
Variable	Percentage of subjects who prefer study medication to previous migraine medications	
Intercurrent Events	Observed analysis. No accounting for intercurrent events.	
Pop. Summary	Percentage within each treatment group (BHV3000 & Placebo)	
Objectives	Pain Relief, on a 4 point scale, at all time points	
Population	mITT	
Variable	Percent of subjects who report pain as none, mild, moderate or severe	
Intercurrent Events	NC=F; RM=F	
Pop. Summary	Percentage of each response, in each treatment group (BHV3000 & Placebo)	
Objectives	Migraine Quality of Life Questionnaire	
Population	mITT	
Variable	Total score on the MQoLQ	
Intercurrent Events	Observed analysis. No accounting for intercurrent events.	
Pop. Summary	Average total score within each treatment group (BHV3000 & Placebo)	
Objective	Safety and Tolerability	
Population	All treated subjects	
Variables	Multiple	
Intercurrent Events	Subjects analyzed as treated. No accounting for intercurrent events	
Pop. Summary	Multiple (discussed under Section 6, "Safety Analyses")	
Objective	Sheehan Suicidality Tracking Scale	
Population	All treated subjects	
Variables	Change from baseline in the total score	
Intercurrent Events	Subjects analyzed as treated. No accounting for intercurrent events	
Pop. Summary	Percentage of subjects, by treatment group, in each of 5 categories ($<-1, -1$, no change, 1, >1)	

Table 3: Estimands for the Exploratory Efficacy Objectives

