14.2.3.8.10	Functional Disability Scale at Every Timepoint Post Dose:	mITT Subjects	
	Exploratory Analysis		
14.2.3.8.11	Sheehan-Suicidality Tracking Scale: Exploratory Analysis	mITT Subjects	
14.2.3.9.1	Kaplan-Meier Time to Pain Freedom: Exploratory Analysis	mITT Subjects	Y
14.2.3.9.2	Median Time to Pain Freedom	mITT Subjects	Y
14.3.1.1	Self-Reported Exposure Data Summary	All Randomized Subjects	
14.3.1.2	Drug Accountability Data Summary	All Randomized Subjects	
14.3.1.3	Cross Tabulation of Exposure and Accountability Data	All Randomized Subjects	
14.3.2.1	Summary of On-Study Adverse Events	Treated Subjects	Y
14.3.2.2	Incidence of On-study Adverse Events by System Organ Class and	Treated Subjects	Y
	Preferred Term		
14.3.2.3	Incidence of On-study Adverse Events Related to Study Drug by	Treated Subjects	
	System Organ Class and Preferred Term		
14.3.2.4	Incidence of On-study Serious Adverse Events by System Organ	Treated Subjects	Y
	Class and Preferred Term		
14.3.2.5	Incidence of On-study Adverse Events with Severe Grade by System	Treated Subjects	
	Organ Class and Preferred Term		
14.4.1.1	Hematology (SI Units): Observed and Change From Baseline Values	Treated Subjects	
	by Visit		
14.4.1.2	Hematology (UI Units): Observed and Change From Baseline	Treated Subjects	
	Values by Visit		
14.4.2.1	Serum Chemistry (SI Units): Observed and Change From Baseline	Treated Subjects	
1 4 4 9 9	Values by Visit	T 1011	
14.4.2.2	Serum Chemistry (US Units): Observed and Change From Baseline	Treated Subjects	
14421	Values by Visit	T 10.11	
14.4.3.1	Hematology (SI Units): Shift from Baseline by Visit	Treated Subjects	Y
14.4.3.2	Hematology (US Units): Shift from Baseline by Visit	Treated Subjects	Y
14.4.4.1	Serum Chemistry (SI Units): Shift from Baseline by Visit	Treated Subjects	Y
14.4.4.2.	Serum Chemistry (US Units): Shift from Baseline by Visit	Treated Subjects	Y
14.4.5.1	Urinalysis (SI Units): Shift from Baseline by Visit	Treated Subjects	
14.4.5.2	Urinalysis (SI Units): Shift from Baseline by Visit	Treated Subjects	

Table Number	Title	Population	Topline
14.4.6.1	Transaminases (SI Units): Shift from Baseline by Visit	Treated Subjects	Y
14.4.6.2	Transaminases (SI Units): Shift from Baseline by Visit	Treated Subjects	Y
14.4.7	Summary of On-Study Liver Toxicity	Treated Subjects	Y
14.5.1	Vital Signs and Physical Measurements: Observed and Change from Baseline Values by Visit	Treated Subjects	

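### SAP 5.7.6.6 summarises only self-reported S-STS scores although the schedule makes the scale clinician administered, and the S-STS table is set to mITT instead of treated subjects

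*SAP*

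**What the plan says.** On the mode of completion:

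- Footnote 8 to protocol Table 1, repeated in SAP Appendix 2: "This scale will be clinician administered, completed on site, and will be in paper".
- Protocol 6.2.5: "The Sheehan STS is a prospective, patient self-reported or clinician administered rating scale that contains 16 questions".
- Protocol 6.1, on how patient ratings are captured: "Electronic Patient Reported Outcomes (ePRO) will be used for all patient-rated scales and will be captured on an eDiary".
- SAP 5.7.6.6: "The S-STS is a prospective, self-reported rating scale that contains 16 questions to track both treatment-emergent suicidal ideation and behaviors". It then adds a second form: "In the event the subject is unavailable, the S-STS clinician-administered rating scale will be completed that contains 6 yes/no questions".
- The scoring rules in SAP 5.7.6.6 are given for self-reported scores only, and so is the summary: "The self-reported S-STS ideation subscale, behavior subscale, and total score will be summarized at baseline", with change from baseline in five categories at end of treatment.

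On the population: the "Sheehan Suicidality Tracking Scale" entry in SAP Table 3 (Section 2.3.3) names all treated subjects. SAP Section 6 runs safety analyses on the treated population. In SAP Appendix 1, Table 14.2.3.8.11, "Sheehan-Suicidality Tracking Scale: Exploratory Analysis", is assigned to mITT subjects. Listing 16.2.11.6 covers S-STS results for all subjects.

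**The concern.** The SAP disagrees with the protocol schedule and with its own Appendix 2 about who completes the scale. Its scoring and summary are attached to the mode that the schedule does not name. A programmer who follows 5.7.6.6 to the letter would leave clinician-administered scores out of the only S-STS summary table. The fallback form has no scoring rule and no table at all.

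The population conflict acts on the same table. mITT membership depends on having efficacy data, which should not decide who is counted in a suicidality summary.

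Because few positive scores are expected, each omission matters. Protocol exclusion criterion 6(e) excludes a score above 0 for the 30 days before Screening and during the study. Baseline totals should therefore be 0 for almost everyone, and the two categories for a decrease should be nearly empty. The information in the table lies in the few subjects who become positive.

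**Working it through.** No sample size, power or alpha figure is involved, so the check sets the texts side by side and counts items.

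**1. Mode.** Footnote 8 fixes mode, place and medium: clinician, site, paper. Protocol 6.1 puts all patient-rated scales on the eDiary, so a paper S-STS fits clinician rating better than self-report. Protocol 6.2.5 is the only place that allows either mode, and it describes one 16-question scale. SAP 5.7.6.6 calls that 16-question scale self-reported and keeps clinician administration for a different, 6-item form. The conflict is therefore both between the documents and within the SAP.

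**2. Can the fallback form give the planned scores?** From the scoring rules in SAP 5.7.6.6:

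- Ideation: Questions 2 to 11 are 11 − 2 + 1 = 10 items scored 0–4, so the range is 0 to 10 × 4 = 40.
- Behavior: 5 components scored 0–4, so the range is 0 to 5 × 4 = 20.
- Total: 0 to 40 + 20 = 60.

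Six yes/no answers cannot supply 10 + 5 = 15 components graded 0–4. Fallback forms need their own tabulation, and none is planned.

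**3. What the summary covers under each reading.**

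- Clinicians administer the 16-question scale and the self-reported label is read loosely: the scores are derived and summarised, and only fallback forms are missing.
- Clinicians administer the 16-question scale and the label is read literally: the scores could be derived but are left out, together with the fallback forms.
- Patients complete the 16-question scale themselves: the scores are summarised, fallback forms are missing, and footnote 8 was not followed.

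The fallback form is unsummarised under all three readings.

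**4. Other outputs.** Table 14.2.3.8.11 is the only S-STS summary in SAP Appendix 1, and Appendices 3 and 4 add none. The safety outcome measures named in SAP Section 6 do not include the S-STS. Listing 16.2.11.6 would show the data but makes no comparison by arm.

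**5. Population.** Under SAP 4.1, mITT requires a single randomization, intake of study medication, a moderate to severe baseline migraine, and at least one post-baseline efficacy value. Treated subjects need only have taken study therapy. Setting the table to mITT therefore drops three groups of treated subjects: those re-randomized, those without a qualifying baseline migraine, and those without post-baseline efficacy data. The likely source is placement: 5.7.6.6 sits in the efficacy chapter, whose default in SAP 5.7 is mITT unless otherwise noted. Table 3 does note otherwise, and the protocol schedule lists the scale under safety assessments.

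**6. Item numbers.** The scoring uses Questions 2–11 (10 labels) plus 1a, 12, 14, 15, 16, 17 and 20 (7 labels). That is 10 + 7 = 17 distinct labels for a scale described as having 16 questions.

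**The case against.** The strongest reply is that protocol 6.2.5 describes one 16-question instrument with two modes, and that footnote 8 names a mode without naming another form. Clinician administration of that scale would still yield every score in 5.7.6.6, and the fault would shrink to a wrong label and an unscored fallback sentence. This stands as a limit on the consequence. It does not remove the conflict, because the SAP text still restricts scoring and summary to self-reported scores.

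A second reply is that suicide risk is caught elsewhere. Under protocol 6.2.5, a subject judged at risk has the event recorded as an AE or SAE, and SAP 6.2 tabulates AEs and SAEs. The S-STS data are also listed for all subjects. This stands too: what may be missing is the score summary, not the events or the data.

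A third reply is that the population conflict is one cell in a table list, against an estimand table that is right. That is so, but the cell determines who is counted in the output.

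A reader might also infer stronger points that the documents do not support:

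- That every scheduled form falls outside the summary, or that the suicidality objective cannot be answered. This needs either the most literal reading of the label or footnote 8 to mean the 6-item form. Footnote 8 does not say that, and 5.7.6.6 keeps that form for an unavailable subject, which fits poorly with completion on site.
- That fallback forms represent the gravest cases. Neither document says why a subject would be unavailable or how many such forms are expected.
- That the scoring refers to questions that do not exist. Labels such as 1a, and the use of rows within questions, show that numbering need not equal the number of questions. The instrument itself is not in the documents, so this is a query only.

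**Conclusion.** The point holds in a limited form. SAP 5.7.6.6 conflicts with footnote 8, with SAP Appendix 2 and with protocol 6.2.5 on the mode of completion. Read literally, it keeps clinician-administered scores out of the only S-STS summary table, and on any reading it leaves the fallback form out. Table 14.2.3.8.11 also uses a narrower population than SAP Table 3 and the treated population that Section 6 sets for safety.

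The size cannot be given as a count. The documents state neither the number of clinician-administered or fallback forms, nor the number of treated subjects outside mITT, nor the number of positive responses. How many scores are lost depends on which form sites used and how literally the label is programmed. The consequence is confined to an exploratory, descriptive summary with no planned test, so the co-primary tests, power and type I error are unaffected. It merits correction because it decides who is counted in a safety output and is cheap to put right.

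**What to change.** - Reconcile SAP 5.7.6.6 with footnote 8 and protocol 6.2.5, and state which form and mode were collected.
- Drop the self-reported restriction, and score and summarise the 16-question scale whichever mode was used.
- Tabulate by arm, separately from the scores, the subjects with any positive response on the 6-item fallback form.
- Confirm the scored item numbers, including Questions 17 and 20, against the form used.
- Change the population of Table 14.2.3.8.11 from mITT to treated subjects. SAP Section 6 already says how re-randomized subjects are assigned to a treatment group for safety.

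The cost is a paragraph of SAP text and one table shell. No new data are needed.
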